The primary efficacy analysis will be performed using an analysis of covariance (ANCOVA). For this analysis, all dose levels for a treatment will be combined into one treatment group for each drug. Separate models will be used for saxagliptin and dapagliflozin analyses, and each analysis will include the (common) placebo control. Each model will have terms for baseline value, treatment group, and randomization strata. Point estimates and 95% confidence intervals will be calculated based on maximum likelihood for the adjusted mean changes within each treatment group as well as for the differences in adjusted mean changes between treatment groups.

The intent-to-treat estimand (which will be estimated using all available data regardless of premature treatment discontinuation and regardless of rescue therapy initiation) will be evaluated as the primary estimand. Missing values for Week 26 will be imputed using a multiple imputation method assuming the data are not missing at random. Multiple imputation using retrieved drop-outs will be used if there is sufficient data from 'retrieved drop-outs', defined as subjects who discontinued the treatment (but not the study) and had a Week 26 HbA1c value. The details of the imputation methods will be presented in the statistical analysis plan.

To assess the robustness of the primary efficacy analysis for the change in HbA1c from baseline to Week 26, additional sensitivity analysis may be performed using the Evaluable Subjects Data Set if > 10% of the subjects in any treatment group in the Randomized Subjects Data Set have relevant protocol deviations.

The primary endpoint will also be compared between the low-dose/high-dose treatment regimen and placebo, separately for both dapagliflozin and saxagliptin. In addition, up-titrating to high-dose and continuing on low-dose will be compared in the subset of dapagliflozin and saxagliptin subjects who had $HbA1c \ge 7\%$ at Week 12. These analyses are described under secondary efficacy analyses.

Secondary efficacy analyses will also be performed separately for each drug (dapagliflozin and saxagliptin). For each drug, the following sequential testing order will be employed to control multiplicity of testing for the secondary objectives.

- Comparison of mean reduction in HbA1c from baseline at Week 26 between the low-dose/high-dose treatment regimen and placebo

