For each drug, a weighted ANCOVA will be performed for the change from baseline in HbA1c at Week 26 to compare the placebo and the low-dose treatment regimen. For this analysis, all dapagliflozin and saxagliptin subjects who had HbA1c < 7% at Week 12 and remained on the low-dose will be get a weight of one. The dapagliflozin and saxagliptin subjects who had HbA1c \geq 7% at Week 12 and continued on the low-dose will get a weight of 2. The dapagliflozin and saxagliptin subjects who had HbA1c \geq 7% at Week 12 and received the high-dose will get a weight of 0. All subjects who do not undergo the second randomization and all placebo subjects will get a weight of one.

For subjects on dapagliflozin and saxagliptin who had $HbA1c \ge 7\%$ at Week 12, the change from baseline HbA1c at Week 26 (ST) will be compared between the subjects re-randomized to remain on the low-dose and the subjects who are re-randomized to the high-dose using an ANCOVA. This analysis will be based on the Up-titration Randomized Subjects Data Set.

Change from baseline at Week 26 (ST) in FPG will be analyzed similarly as the analyses of change from baseline in HbA1c at Week 26.

The proportion of subjects achieving HbA1c < 7.0% at Week 26 (ST) will be analyzed using weighted logistic regression with adjustment for the baseline HbA1c measurement and the randomization strata. Weighting for the subjects will be applied similarly to a weighting in the analysis of change from baseline in HbA1c. Subjects with missing a response at Week 26 will be imputed by dichotomizing the imputed values of HbA1c at Week 26.

The assessment of safety will be based on the analyses of AEs, vital signs, physical examinations, electrocardiograms, hypoglycemia events, DKA events, safety laboratory evaluations, and measures of growth and maturity. Dapagliflozin and saxagliptin will be summarized separately. Both low-dose and high-dose saxagliptin and dapagliflozin groups, respectively, will be combined for saxagliptin and dapagliflozin to provide the safety summary for overall saxagliptin and overall dapagliflozin compared to placebo. A common placebo group will be included in each summary.

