4.1.7.3 Handling of implausible glucose results

It was identified prior to Week 56 database lock during ongoing data review that there was an implausible FPG value recorded for one subject at their Day 1 visit. This was investigated and confirmed by the central laboratory and it was decided that the results will be used in the primary analysis.

A sensitivity analysis of the secondary efficacy endpoints for FPG excluding this result and any other outliers may be conducted post-Week 56 database lock, if deemed necessary.

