4.1.9 Weighted analysis of covariance (ANCOVA)

In summaries of primary and secondary efficacy endpoints examining the change from baseline at Week t , an ANCOVA model of the differences between Week t and baseline measurements will be used, controlling for baseline value as a covariate, and treatment group (regimen) and randomisation strata as fixed effects. Only main effects of the randomisation strata will be included in the model. The model will have the following form:

$$D_{t,ijm} = \text{intercept} + \beta [Y_{0,ijm}] + \tau_j + \omega_m + \text{error}_{ijm}$$

where:

- $D_{t,ijm} = Y_{t,ijm} - Y_{0,ijm}$ = the Week t change from baseline of subject i in treatment group j and stratum m .
- $Y_{0,ijm}$ is the baseline measurement of subject i in treatment group j and in strata m ,
- $Y_{t,ijm}$ is the Week t measurement of subject i in treatment group j and in strata m ,
- β is the slope of $D_{t,ijm}$ regressing on the baseline measurement,
- τ_j is the mean effect of treatment group j ,
- ω_m is the mean effect of randomisation stratum m ,
- *Intercept*, β and τ_j are unknown parameters to be estimated from the data.

Weights will be used in the ANCOVA model to test the treatment regimens compared to placebo, $\mathbf{H}_{01}: \tau_{TR1} - \tau_{Pla} = 0$ and $\mathbf{H}_{02}: \tau_{TR2} - \tau_{Pla} = 0$.

The weight matrices to test hypotheses \mathbf{H}_{01} and \mathbf{H}_{02} are denoted by \mathbf{W}_1 and \mathbf{W}_2 respectively, defined as follows:

$$\mathbf{W}_1 = \text{Diag} \begin{bmatrix} \mathbf{1}_{1 \times n} \\ \mathbf{1}_{1 \times rn} \\ \mathbf{2}_{1 \times (1-r)n/2} \\ \mathbf{0}_{1 \times \frac{(1-r)n}{2}} \end{bmatrix} \quad \mathbf{W}_2 = \text{Diag} \begin{bmatrix} \mathbf{1}_{1 \times n} \\ \mathbf{1}_{1 \times rn} \\ \mathbf{0}_{1 \times \frac{(1-r)n}{2}} \\ \mathbf{2}_{1 \times (1-r)n/2} \end{bmatrix}$$

where r is the proportion of response (HbA1c < 7%), n is the number of subjects within an arm, and based on a 1:1:1 randomisation.

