4.1.12.2 Retrieved Drop-Outs Multiple Imputation Method

Missing HbA1c/FPG data will be imputed separately by treatment regimen of each drug (i.e., low-dose, low-dose/high-dose, and placebo) and weight (as applicable). Subjects not going through up-titration randomisation due to discontinuation of study medication will be assigned a weight of 1 and imputed in the both the low-dose and low-dose/high-dose regimens.

Using monotone datasets generated as described in Section 4.1.12.1, the remaining missing HbA1c/FPG data will be imputed separately for each treatment group and weight (as applicable) using a REGRESSION method in conjunction with the MONOTONE statement and the MNAR statement of the SAS MI procedure.

- Step 1: The imputation model used to create monotone data pattern (see Section 4.1.12.1) will include factors and covariates in the following order: indicators representing randomisation strata of sex, age group and background medication, baseline HbA1c/FPG as well as HbA1c/FPG from all visits per protocol up to Week t.
- Step 2: Using an imputation model with terms for indicators representing randomisation strata of sex, age group and background medication, baseline HbA1c/FPG followed by Week t HbA1c/FPG, for each treatment regimen and weight, subjects that discontinue treatment prior to Week t with baseline and an (off-treatment) Week t assessment available will be used to impute within each missing Week t values (for that treatment regimen) after baseline. Separate models will be performed for each treatment regimen and weight (as applicable) to impute Week t missing data in the multiply imputed monotone datasets generated by Step 1. For this step, one imputation will be performed for each of the 200 imputed datasets from Step 1 to form “complete datasets”.
- Step 3: Imputed values from each of the 200 imputation datasets selected from Step 2 and the non-missing data will be used to calculate change from baseline. The HbA1c/FPG change from baseline values at Week t will be analysed by an ANCOVA with terms for baseline HbA1c/FPG, randomisation strata, and treatment group as described in Section 4.1.9. In case of non-convergence, the imputation and ANCOVA model will be simplified by removing/collapsing the randomisation strata indicator variables in a stepwise manner as described in Section 4.1.

- Step 4: Results from each ANCOVA model will be combined as described in Section 4.1.12.4.

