4.4 Primary efficacy endpoint analysis

4.4.1 Primary analysis of the primary endpoint

The primary efficacy analysis will compare the mean reduction in HbA1c from baseline at Week 26 between overall drug treatment (low-dose and high-dose) and placebo. The ITT estimand (which will be estimated using data regardless of premature treatment discontinuation, regardless of rescue medication initiation and with multiple imputation) will be evaluated as the primary estimand.

Listings of HbA1c and FPG results used for the efficacy analysis will be presented with flags to identify data collected prior to rescue medication initiation or treatment discontinuation.

The primary efficacy analysis will be performed using an ANCOVA model, as described in Section 4.1.9. Separate models will be used for dapagliflozin and saxagliptin analyses, and each analysis will include the (common) placebo control. Each model will have terms for baseline HbA1c value, treatment group, and randomisation strata variables (age group, sex and background medication). Missing values for Week 26 will be imputed using multiple imputation method assuming the data are not missing at random. No weights will be used in the multiple imputation or ANCOVA for this analysis.

An overview of the analysis steps are as follows:

- i) Impute missing Week 26 HbA1c data using multiple imputation (as described in Section 4.1.12).
- ii) Analyse data by applying the ANCOVA model (described in Section 4.1.9) in each of the imputed data sets to calculate the LS means and corresponding SEs for the adjusted mean changes within each treatment group as well as for the differences in adjusted mean changes

between treatment groups. If any stratification variables in the imputation model are collapsed, then the ANCOVA model will be collapsed correspondingly.

- iii) Combine point estimates and SEs using Rubin's rules (as per Section 4.1.12.4) to produce valid global estimates with corresponding p-values and CIs.

Combined LS means and 95% confidence intervals for the mean change in HbA1c for each treatment group as well as the difference in the estimated mean change between the dapagliflozin/saxagliptin treatment group and placebo will be calculated. The p-value of the difference in Week 26 estimates between dapagliflozin/saxagliptin and placebo will be presented.

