Data will be multiply imputed based on the same approach as described for the primary analysis of the primary endpoint in Section 4.4.1 at all scheduled time points up to and including Week 26, replacing HbA1c with FPG, and will include all data regardless of rescue medication initiation or adherence. Only FPG assessments documented with the subject in a fasting state will be summarised and listed. Analysis will be performed by fitting the ANCOVA model described for the primary analysis of the primary endpoint in Section 4.4.1 (replacing HbA1c with FPG). The analysis model will be evaluated in each imputed data set and the results will be combined using Rubin's rules as described in Section 4.1.12.4. No weights will be used in the multiple imputation or ANCOVA for this analysis.

In addition, a line plot of LS mean \pm 95% confidence interval (CI) by visit up to Week 26 will be displayed.

4.5.4.1 Sensitivity analysis for secondary endpoint of mean reduction in FPG from baseline at Week 26 between overall drug treatment and placebo excluding data following rescue medication initiation/early treatment discontinuation

The above primary analysis (Section 4.5.4) for the comparison of mean reduction in FPG from baseline at Week 26 between overall drug treatment (low-dose and high-dose) and placebo will be repeated excluding data following rescue medication initiation or early treatment discontinuation but missing data will be imputed assuming MAR as described in Section 4.1.12.5.

4.5.4.2 Metformin subgroup analysis for comparison of mean reduction in FPG from baseline at Week 26 between overall drug treatment and placebo

The ANCOVA model used for the primary FPG analysis (Section 4.5.4) of the change from baseline in FPG at Week 26 between overall drug treatment and placebo will also be repeated for the subgroup of subjects on a stable baseline dose of metformin IR or XR (with or without insulin). The same multiple imputation method used for the primary analysis of the endpoint will be used for this subgroup analysis. The indicator for background medication used in the multiple imputation step for insulin only and insulin with metformin will be grouped as defined in Section 4.1.12. No weights will be used in the multiple imputation or ANCOVA for this analysis.

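### The FPG models in the confirmatory sequence omit baseline HbA1c, which is already collected; adding it is a cheap option that could narrow the FPG intervals by an unknown amount

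*Protocol*

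**What the plan says.** Protocol 8.4.2.1 sets the terms of the HbA1c ANCOVA: "Each model will have terms for baseline value, treatment group, and randomization strata". For FPG, the synopsis and section 8.4.2.2 say "Change from baseline at Week 26 (ST) in FPG will be analyzed similarly as the analyses of change from baseline in HbA1c".

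SAP 4.1.9 gives the general model as "controlling for baseline value as a covariate, and treatment group (regimen) and randomisation strata as fixed effects". SAP 4.4.1 spells out the terms beside baseline HbA1c as "treatment group, and randomisation strata variables (age group, sex and background medication". SAP 4.5.4 (test 3, overall drug against placebo) specifies "fitting the ANCOVA model described for the primary analysis of the primary endpoint in Section 4.4.1 (replacing HbA1c with FPG". Sections 4.5.5 and 4.5.6 (tests 4 and 5) use the weighted form of the same model, and 4.5.11 (test 10, high against low dose in the re-randomised subset) the unweighted form. After retrieved drop-out imputation, SAP 4.1.12.2 analyses each data set by "an ANCOVA with terms for baseline HbA1c/FPG, randomisation strata, and treatment group". In each case baseline FPG takes the place of baseline HbA1c; it does not join it.

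On data collection, Protocol Table 5.1-1 has no FPG at screening or lead-in, and Table 5.1-2 has one pre-dose FPG sample on Day 1. HbA1c is scheduled at screening and again on Day 1. SAP 4.1.7.3 reports "an implausible FPG value recorded for one subject at their Day 1 visit", confirmed by the central laboratory and kept in the primary analysis.

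Under SAP 4.5.1, testing for each drug stops at the first secondary test that is not significant.

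**The concern.** One fasting glucose reading reflects glycaemia at one moment. The protocol's own rationale for Amendment 05 describes HbA1c as reflecting blood glucose over the preceding three months. Baseline HbA1c may therefore carry information about a child's later FPG that one Day 1 reading does not. Any such information now stays in the residual variance of the FPG model.

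The plan already uses baseline HbA1c in a related setting. Protocol 8.4.2.3 adjusts the Week 26 rescue-or-discontinuation endpoint for it, although before Week 26 the rescue criteria in Table 3.5.2-1 are FPG thresholds only.

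At stake are the width of the FPG intervals and the chance of passing tests 3, 4, 5 and 10. If the primary test and tests 1 and 2 succeed, test 3 stands in front of tests 4 to 11 for that drug.

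**Working it through.** **1. The plan's own figure.** Protocol 8.1 gives 243 subjects in three equal arms (81 per arm), a difference of 0.75%, SD 1.7%, two-sided alpha 0.05 and power of about 80%.

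- Standard error = 1.7 × √(2/81) = 0.267.
- Power = Φ(0.75/0.267 − 1.96) = 0.802; the noncentral t gives 0.797.

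The stated power reproduces, but it is for HbA1c. Neither document gives an SD, effect size or power for FPG, so the 80% used below for FPG is only a nominal starting point.

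**2. Effect of one more baseline covariate.** Let r be the partial correlation of baseline HbA1c with Week 26 FPG, given baseline FPG and the strata. Adding baseline HbA1c multiplies the variance of the treatment difference by

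V = (1 − r²) × (N − k − 2)/(N − k − 3).

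The second factor is the small-sample price of the extra term. For test 3, N = 2 × 81 = 162. The model has k = 7 parameters: intercept, treatment, baseline FPG, sex, age group and two for background medication. The price is 153/152 = 1.0066, and the residual degrees of freedom go from 162 − 7 = 155 to 154.

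Power = Φ(2.80/√V − 1.96), where 2.80 = 1.96 + 0.84 corresponds to 80%.

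| Assumed r | V | Change in interval width | Power |
|---|---|---|---|
| 0 | 1.007 | +0.3% | 79.7% |
| 0.2 | 0.966 | −1.7% | 81.3% |
| 0.3 | 0.916 | −4.3% | 83.3% |
| 0.4 | 0.845 | −8.0% | 86.1% |

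**3. Break-even.** V = 1 when r² = 1/(N − k − 2).

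- Test 3: r = √(1/153) = 0.08.
- Test 10 uses only subjects re-randomised at Week 14. If 80 are analysed (assumed), r = √(1/71) = 0.12; if 40 (assumed), r = √(1/31) = 0.18.

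Tests 4 and 5 give weight 0 to part of the active arm and weight 2 to another part, so the figures for N = 162 are only a guide there.

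**4. How large might r be?** The documents do not say. As an illustration, take a = corr(baseline FPG, Week 26 FPG) from 0.3 to 0.6, h = corr(baseline HbA1c, Week 26 FPG) from 0.3 to 0.5, and c = corr(baseline FPG, baseline HbA1c) from 0.5 to 0.8. All are assumed, and the strata are ignored. Then r = (h − ac)/√((1 − a²)(1 − c²)).

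- a = 0.5, h = 0.4, c = 0.8: r = 0, variance cut 0%.
- a = 0.3, h = 0.4, c = 0.65: r = 0.205/0.725 = 0.28, cut 8%.
- a = 0.3, h = 0.5, c = 0.8: r = 0.26/0.572 = 0.45, cut 21%.

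Several combinations in this grid give less than 2%. The gain runs from nothing to material.

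**5. Room in the imputation models.** The Week 26 step of the retrieved drop-out model (SAP 4.1.12.2) has six coefficients: intercept, sex, age group, two background-medication indicators and baseline FPG. SAP 4.1.12 allows it to be fitted with as few as five retrieved drop-outs, so it has no room for a seventh. In the wash-out method, missing active-arm values are imputed from the placebo group, and the MAR method uses all non-missing data in the regimen.

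**The case against.** The strongest reply is that nothing here is defective. Protocol and SAP agree, and adjusting an endpoint for its own baseline value and the strata is standard and valid. Which further prognostic covariate to add is then a matter of preference, with a benefit that rests wholly on an assumed r. Entry is also limited to HbA1c of 6.5% to 10.5%, which may weaken the correlation. All of this stands, and it is why the point is no more than an inexpensive option.

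A second reply concerns consistency. Retrieved drop-out imputation is the preferred method. If baseline HbA1c enters the ANCOVA but not that imputation model, imputed Week 26 FPG values carry no relation to HbA1c beyond that through the terms in the model. SAP 4.4.1 takes care to keep the two models aligned when strata are collapsed. This limits the imputation part of the change but does not defeat the ANCOVA part.

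A reader might infer more than the documents support:

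- **That the FPG tests adjust for nothing but one FPG reading.** They also adjust for age group, sex and background medication. Baseline FPG is the only glycaemic covariate, not the only covariate.
- **That a known amount of precision is lost, at no saving.** The loss may be near nil, and the extra term has a price, small for test 3 and larger for test 10.
- **That the retained Day 1 value shows baseline FPG to be unreliable.** It is one laboratory-confirmed result. SAP 4.1.7.3 allows a sensitivity analysis without it, and SAP 4.1.9 commits to influence diagnostics and to further analyses without influential outliers. Adding HbA1c would not take the value out of the model.
- **That the testing sequence will stop at test 3 because of this.** No figure in the documents shows that test 3 is likely to fail, and it is formally tested only if the primary test and tests 1 and 2 have succeeded.

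**Conclusion.** The point holds as a low-cost efficiency improvement. The FPG ANCOVA for tests 3, 4, 5 and 10 leaves out a baseline measurement that the trial already has and uses elsewhere for an endpoint driven by glucose. The planned analysis remains valid without it, and adding it would leave the randomised comparison unbiased.

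For test 3 the trade is lopsided. If baseline HbA1c adds nothing, variance rises by about 0.7% and power falls by about 0.3 points from a nominal 80%. If r is 0.2 to 0.4, power rises by about 1.3 to 6.1 points. These figures rest on the assumed r, the nominal 80%, and 162 analysed subjects. For test 10 the benefit is less certain, because r must exceed about 0.12 to 0.18 before anything is gained if 80 to 40 subjects are analysed.

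**What to change.** Before unblinding:

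- In SAP 4.1.9, state that the FPG ANCOVA includes continuous baseline HbA1c in addition to baseline FPG, treatment and strata, and apply this in 4.5.4, 4.5.5 and 4.5.6. Apply it in 4.5.11 too, recognising the less certain gain there.
- State the same in Protocol 8.4.2.2.
- Add baseline HbA1c to the FPG imputation models under the wash-out method (SAP 4.1.12.3) and under MAR (SAP 4.1.12.5).
- Leave the retrieved drop-out model (SAP 4.1.12.2) unchanged unless there are enough retrieved drop-outs to support another coefficient.

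If unblinding has already taken place, report the adjusted model only as a labelled supplementary analysis.

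The cost is some SAP and protocol wording, one covariate in the code and one degree of freedom, with no new data. Under retrieved drop-out imputation there is also a small mismatch between the imputation and analysis models, which the SAP should acknowledge.

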1 INTRODUCTION AND STUDY RATIONALE

Type 2 diabetes is a complex and multifactorial metabolic disorder with contributions from genetic, behavioral, and environmental risk factors. Despite a wealth of information concerning Type 2 diabetes in adults, data unique to the pediatric age group regarding the pathophysiology of and therapy for Type 2 diabetes are limited.¹

As in adults, Type 2 diabetes in children is characterized by hyperglycemia associated with initial relative insufficiency of insulin secretion and increased insulin resistance, and is ultimately often followed by pancreatic β-cell failure. A potentially important difference between adults and pediatric patients with Type 2 diabetes is that in the natural course of Type 2 diabetes in pediatric patients, the glucose dysregulation may develop over a much more rapid time frame than is seen in adults. This may be a contributing factor to the tendency for poorer prognosis for microvascular and macrovascular diabetic complications for pediatric patients with Type 2 diabetes, as they become adults. An additional factor unique to the development of Type 2 diabetes in the pediatric age range is the potential additive contribution and impact of the insulin resistance of puberty, which, although a natural phenomenon during pubertal development, may have a negative influence on and potentially exacerbate glycemic dysregulation in susceptible children.

As with adults, it is expected that children and adolescents with Type 2 diabetes are at risk for eventually developing diabetes-related micro- and macrovascular complications with higher glycemic levels. Data from a number of small studies conducted in limited ethnic groups have confirmed an increased risk of microvascular complications 1,7 in pediatric patients with Type 2 diabetes compared with children and adolescents without diabetes. For example, microalbuminuria, macroalbuminuria, and hypercholesterolemia have all shown an increased tendency to develop in Pima Indian children with Type 2 diabetes. Among Japanese pediatric patients, retinopathy has been observed at a similar rate in those with Type 1 and Type 2 diabetes, although it appears to be less common in pediatric patients compared with adults with Type 2 diabetes. A study in Australia found that pediatric patients with Type 2 diabetes have significantly higher rates of microalbuminuria and hypertension than those with Type 1 diabetes, despite shorter duration of disease and lower glycosylated hemoglobin (HbA1c). Additional small studies have shown an increased occurrence of renal disease (Japanese), non-alcoholic fatty liver disease (the Manitoba Cree), and cardiovascular mortality associated with hypertension and dyslipidemia in pediatric patients with Type 2 diabetes.

There is evidence in adults from the UK Prospective Diabetes Study (UKPDS) that normalization of blood glucose substantially decreases the frequency of microvascular complications of Type 2 diabetes (UKPDS Group 1998), consistent with what has been noted with Type 1 diabetes. ¹⁰ It is assumed that a management regimen based on adequate glycemic control, via lifestyle changes with modification of diet and physical activity and, as appropriate, medical treatment, should help to reduce the risk of complications in younger persons as well as adults with the disease.

Current therapeutic agents have limited efficacy and are associated with side effects including hypoglycemia, weight gain, edema and gastrointestinal effects. While there are several oral glucose-lowering medications approved for adults with Type 2 diabetes, the only oral

glucose-lowering medication approved for use in pediatric patients age 10 and older is metformin. Agents with new mechanisms of action for the treatment of Type 2 diabetes are being studied.

Given the need for additional oral glucose-lowering therapy options for pediatric patients with Type 2 diabetes, it is appropriate to test the hypothesis that saxagliptin, an orally active dipeptidyl-peptidase-4 (DPP-4) inhibitor, and dapagliflozin, an orally active sodium glucose cotransporter-2 (SGLT-2) inhibitor, will confer the therapeutic benefit of glucose-lowering, without adding the risk of hypoglycemia, in this population. In addition, the risk of weight gain is not expected with saxagliptin, while dapagliflozin is expected to confer some weight loss. This program will investigate the pharmacokinetics (PK), efficacy, safety, and tolerability of saxagliptin versus placebo, and separately, dapagliflozin versus placebo for the treatment of Type 2 diabetes in pediatric patients aged from 10 to < 18 years.

